7. RESTRICTIONS DURING THE STUDY AND CONCOMITANT TREATMENT(S)

7.1 Restrictions during the study

The following restrictions apply while the patient is receiving study treatment and for the specified times before and after:

Female patient of child-bearing potential

- Female patients of childbearing potential who are not abstinent and intend to be sexually active with a non-sterilized male partner must use at least 1 **highly** effective method of contraception (Table 3) from the time of screening throughout the total duration of the drug treatment and the drug washout period (90 days after the last dose of durvalumab monotherapy). Non-sterilised male partners of a female patient of childbearing potential must use male condom plus spermicide throughout this period. Cessation of birth control after this point should be discussed with a responsible physician. Periodic abstinence, the rhythm method, and the withdrawal method are not acceptable methods of birth control. Female patients should also refrain from breastfeeding throughout this period.

Male patients with a female partner of childbearing potential

- Non-sterilized male patients who are not abstinent and intend to be sexually active with a female partner of childbearing potential must use a male condom plus spermicide from the time of screening throughout the total duration of the drug treatment and the drug washout period (90 days after the last dose of durvalumab monotherapy). However, periodic abstinence, the rhythm method, and the withdrawal method are not acceptable methods of contraception. Male patients should refrain from sperm donation throughout this period.
- Female partners (of childbearing potential) of male patients must also use a highly effective method of contraception throughout this period (Table 3).

N.B Females of childbearing potential are defined as those who are not surgically sterile (ie, bilateral salpingectomy, bilateral oophorectomy, or complete hysterectomy) or post-menopausal.

Women will be considered post-menopausal if they have been amenorrheic for 12 months without an alternative medical cause. The following age-specific requirements apply:

- Women <50 years of age would be considered post-menopausal if they have been amenorrheic for 12 months or more following cessation of exogenous hormonal treatments and if they have luteinizing hormone and follicle-stimulating hormone levels in the post-menopausal range for the institution.
- Women ≥50 years of age would be considered post-menopausal if they have been amenorrheic for 12 months or more following cessation of all exogenous hormonal treatments, had radiation-induced menopause with last menses >1 year ago, had chemotherapy-induced menopause with last menses >1 year ago.

Highly effective methods of contraception, defined as one that results in a low failure rate (ie, less than 1% per year) when used consistently and correctly are described in Table 3. Note that some contraception methods are not considered highly effective (e.g. male or female condom with or without spermicide; female cap, diaphragm, or sponge with or without spermicide; non-copper containing intrauterine device; progestogen-only oral hormonal contraceptive pills where inhibition of ovulation is not the primary mode of action [excluding Cerazette/desogestrel which is considered highly effective]; and triphasic combined oral contraceptive pills).

Table 3. Highly Effective Methods of Contraception (<1% Failure Rate)

• Barrier/Intrauterine methods	• Hormonal Methods
• Copper T intrauterine device	• Implants: Etonogestrel-releasing implants: e.g. Implanon® or Norplant®
• Levonorgestrel-releasing intrauterine system (e.g., Mirena®) ^a	• Intravaginal: Ethinylestradiol/etonogestrel-releasing intravaginal devices: e.g. NuvaRing®
	• Injection: Medroxyprogesterone injection: e.g. Depo-Provera®
	• Combined Pill: Normal and low dose combined oral contraceptive pill
	• Patch: Norelgestromin/ethinylestradiol-releasing transdermal system: e.g. Ortho Evra®
	• Minipill: Progesterone based oral contraceptive pill using desogestrel: Cerazette® is currently the only highly effective progesterone-based

^a This is also considered a hormonal method

Blood donation

Patients should not donate blood while participating in this study, or for at least 90 days following the last infusion of durvalumab.

7.2 Concomitant treatment(s)

Concomitant therapy includes any medication (e.g., prescription drugs, over-the-counter drugs, vaccines, herbal or homeopathic remedies, nutritional supplements) used by a patient from 7 days prior to initiation of study drug to the study completion/ discontinuation visit. Because there is a potential for interaction of sirolimus with other concomitantly administered drugs through the cytochrome P450 system, the case report form must capture the concurrent use of all other drugs, over-the-counter medications, or alternative therapies. The Principal Investigator should be alerted if the patient is taking any agent known to affect or with the potential to affect selected CYP450 isoenzymes. Appendix 4 presents guidelines for identifying medications/substances that could potentially interact with the study agent(s).

7.2.1 Permitted concomitant medications

Table 4. Permitted Supportive Medications

Supportive medication/class of drug:	Usage:
Concomitant medications or treatments (e.g., acetaminophen or diphenhydramine) deemed necessary to provide adequate prophylactic or supportive care, except for those medications identified as “prohibited,” as listed above	To be administered as prescribed by the Investigator
Best supportive care (including antibiotics, nutritional support, correction of metabolic disorders, optimal symptom control, and pain management [including palliative radiotherapy to non-target lesions, etc.])	Should be used, when necessary, for all patients
Inactivated viruses, such as those in the influenza vaccine	Permitted
Inhaled steroids for COPD, mineralocorticoids (eg fludrocortisone for adrenocortical insufficiency), and prednisone < 10mg daily	Permitted

Clinical Study Protocol

Investigational Drug Substance: MEDI4736 Sirolimus (Rapamune)

Study Number **19-20015**

Edition Number: 4

Date: **11 February 2022**

Standard-of-Care Chemotherapy (with or without Radiation) after Surgical Resection

After surgical resection of their tumor, patients may receive SOC chemotherapy (with or without radiation) after surgical resection of their tumor. Choice of SOC adjuvant therapy will be at the discretion of the treating physician, depending on the stage of their disease, as deemed clinically appropriate.

7.2.2 Excluded concomitant medications

Table 5. Prohibited Concomitant Medications

Prohibited medication/class of drug:	Usage:
Any investigational anticancer therapy other than those under investigation in this study	Should not be given concomitantly whilst the patient is on study treatment
mAbs against CTLA-4, PD-1, or PD-L1 other than those under investigation in this study	Should not be given concomitantly whilst the patient is on study treatment
Any concurrent chemotherapy, radiotherapy, immunotherapy, or biologic or hormonal therapy for cancer treatment other than those under investigation in this study	Should not be given concomitantly whilst the patient is on study treatment. (Concurrent use of hormones for non-cancer-related conditions [e.g., insulin for diabetes and hormone replacement therapy] is acceptable. Local treatment of isolated lesions, excluding target lesions, for palliative intent is acceptable [e.g., by local surgery or radiotherapy])
Immunosuppressive medications including, but not limited to, systemic corticosteroids at doses exceeding 10 mg/day of prednisone or equivalent, methotrexate, azathioprine, and tumor necrosis factor- α blockers	Should not be given concomitantly, or used for premedication prior to the I-O infusions. The following are allowed exceptions: 
• Use of immunosuppressive medications for the management of IP-related AEs,• Use in patients with contrast allergies.• In addition, use of inhaled, topical, and intranasal corticosteroids is permitted. A temporary period of steroids will be allowed if clinically indicated and considered to be essential for the management of non-immunotherapy related events experienced by the patient (e.g., chronic obstructive pulmonary disease, radiation, nausea, etc.).

Clinical Study Protocol

Investigational Drug Substance: MEDI4736 Sirolimus (Rapamune)

Study Number **19-20015**

Edition Number: 4

Date: **11 February 2022**

Prohibited medication/class of drug:	Usage:
EGFR TKIs	Should not be given concomitantly. Should be used with caution in the 90 days post last dose of durvalumab. Increased incidences of pneumonitis (with third generation EGFR TKIs) and increased incidence of transaminase increases (with 1 st generation EGFR TKIs) has been reported when durvalumab has been given concomitantly.
Live attenuated vaccines	Should not be given through 30 days after the last dose of IP (including SoC)
Herbal and natural remedies which may have immune-modulating effects	Should not be given concomitantly unless agreed by the sponsor
Seville orange, star fruit, grapefruit and their juices	Should not be used concomitantly as they affect P450 and P glycoprotein (P-gp) activity.
Strong inhibitors of CYP3A4 or P-GP	Should not be given concomitantly, see table 5
Strong inducers of CYP3A4	Should not be given concomitantly, see table 5
Moderate CYP3A4 inhibitors	Should be used with caution, see table 5

Table 6. List of CYP3A4 strong and moderate inhibitors and inducers

Strong CYP3A4,5,7 inhibitors	Moderate CYP3A4,5,7 inhibitors	CYP3A4 inducers
clarithromycin	aprepitant	Barbiturates
Conivaptan	atazanavir	Carbamazepine
grapefruit juice	cimetidine	Efavirenz
Indinavir	ciprofloxacin	Modafenil
Itraconazole	darunavir	Nevirapine
Ketoconazole	diltiazem	Oxcarbazepine
Lopinavir	erythromycin	Phenobarbital
Mibepradil	fluconazole	Phenytoin
Nefazodone	tofisopam	pioglitazone
Nelfinavir	verapamil	Rifabutin
Posaconazole	amprenavir	Rifampin
Ritonavir	fosamprenavir	St. John's wort
Saquinavir		Topiramate

Clinical Study Protocol

Investigational Drug Substance: MEDI4736 Sirolimus (Rapamune)

Study Number **19-20015**

Edition Number: 4

Date: **11 February 2022**

Strong CYP3A4,5,7 inhibitors	Moderate CYP3A4,5,7 inhibitors	CYP3A4 inducers
Telithromycin		troglitazone
Troleandomycin		
Voriconazole		

This database of CYP inhibitors was compiled from the Indiana University School of Medicine's "Clinically Relevant" Table and from the University of Washington's Drug Interaction Database based on in vitro studies. Strong inhibitors are predicted to increase BKM120 AUC $>$ 5-fold, and moderate inhibitors are predicted to increase BKM120 AUC \geq 2-fold but $<$ 5-fold.
 
This database of CYP inducers was compiled from the FDA's "Guidance for Industry, Drug Interaction Studies;" from the Indiana University School of Medicine's "Clinically Relevant" Table; and from (Pursche et al. 2008).
		

8. STUDY PROCEDURES

8.1 Schedule of study procedures

Before study entry, throughout the study, and following study drug discontinuation, various clinical and diagnostic laboratory evaluations are outlined. The purpose of obtaining these detailed measurements is to ensure adequate safety and tolerability assessments. Clinical evaluations and laboratory studies may be repeated more frequently if clinically indicated. The Schedules of Assessments during the screening and treatment period is provided following the Protocol Synopsis.

- Tumor efficacy (RECIST) assessment dates are not affected by dose delays and remain as originally scheduled, as they are based on the date of surgery.
- All other scheduled assessments must be performed relative to the start of the dosing cycle such that all laboratory procedures, etc. required for dosing should be performed within 3 days prior to dosing.
- Patients may delay durvalumab dosing under certain circumstances.
 - Dosing may be delayed per Toxicity Management Guidelines, due to either an immune or a non-immune-related AE.
 - If dosing must be delayed for reasons other than treatment-related toxicity, dosing will resume as soon as feasible

8.1.1 Screening phase

Screening procedures will be performed up to 35 days before Day -7, unless otherwise specified. All patients must first read, understand, and sign the IRB approved ICF before any study-specific screening procedures are performed. After signing the ICF, completing all screening procedures, and being deemed eligible for entry, patients will be enrolled in the study. Procedures that are performed prior to the signing of the ICF and are considered standard of care may be used as screening assessments if they fall within the 28-day screening window.

The following procedures will be performed during the Screening Visit:

- Informed Consent
- Review of eligibility criteria
- Medical history and demographics
- Complete physical exam
- ECOG Performance Status
- Vitals signs, weight and height

- 12-lead ECG (in triplicate [2-5 minutes apart])
- Tumor biopsy for fresh tissue if not already obtained
- Review of prior/concomitant medications
- Imaging by CT/MRI
- Clinical laboratory tests for:
 - Hematology (see Table 7)
 - Clinical chemistry (see Table 8)
 - TSH
 - Coagulation (PT, PTT, INR)
 - Creatinine Clearance
 - Serum pregnancy test (for women of childbearing potential only)
 - Hepatitis serologies
 - Urinalysis (see Table 9)

8.1.2 Treatment phase

Procedures to be conducted during the treatment phase of the study are presented in the Schedule of Assessments. Screening procedures performed within 72 hours of cycle 1 day 1 do not need to be repeated on cycle 1 day 1.

1. Sirolimus dosing: will be given 6mg po once on day 1, followed by 2mg po daily on days 2-21. Steady state trough levels will be collected on day 23 and stored for batch analysis.
2. Heavy water dosing: first dose to be taken in clinic on day 23 and a 6 week supply for self- administration will be dispensed in labeled conical tubes. The patients will also be shown how to collect salivate samples.
3. Durvalumab dosing: starting on Day 22 q 3 weeks for 2 doses
4. Restaging imaging prior to surgery
5. Standard of care surgical resection
6. Peripheral blood research tube collection per study calendar

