Edition Number: **4**

Date: **11 February 2022**

- To evaluate the efficacy of sirolimus followed by durvalumab as neoadjuvant treatment for Stage I, II, and IIIA NSCLC

Secondary Objective(s):

- To evaluate the efficacy of sirolimus followed by durvalumab as neoadjuvant treatment for Stage I, II, and IIIA NSCLC
- To evaluate response to sirolimus followed by durvalumab in patients with PD-L1 positive vs. PD-L1-negative tumors
- To evaluate the association between blood mutation burden and response to sirolimus followed by durvalumab

Exploratory Objective(s):

- To evaluate the immune-mediated effects of sirolimus followed by durvalumab
- To investigate tumor and immune microenvironment changes in tissue samples

Study Design:

Up to 31 patients with NSCLC will be enrolled in this study at Emory University Winship Cancer Institute and associated clinical sites. Eligible patients will complete 3 weeks of daily oral sirolimus followed by 2 cycles of durvalumab treatment prior to proceeding to standard of care surgical resection. Durvalumab will be administered at a dose of 1500mg Q 3 weeks starting on C1D1 for up to 2 cycles that are 21 days in length. Pharmacodynamic analysis will be done using PD samples collected at baseline (tissue) and with blood samples on day 1, day 22 C1 prior to durvalumab, day 43 C2 durvalumab, and at the time of surgery (blood and tissue). Additional post surgery blood samples will be collected at 1-, 3-, and 6-months post-surgery. See Appendix D for schedule of Biomarker collection. Patients will proceed to surgery within a 2–3-week period post 2nd dose of durvalumab but not earlier than two weeks after the administration of durvalumab i.e. not earlier than C2D14. Additionally, as an optional study, patients will self-administer heavy water (D2O) 50ml orally three times a day from day 22 C1 through day 27 followed by 50ml orally twice a day through the day prior to surgery in order to label dividing cells for research tracking purposes.

Number of Centers: Emory University Winship Cancer Institute and affiliated hospitals

Number of Patients: 31

Study Population: Resectable Stage 1-3A NSCLC

Inclusion Criteria:

- Pathologically documented NSCLC who are candidates for surgical resection
- Capable of signing informed consent

- Age \geq 18 years at time of study entry.
- Eastern Cooperative Oncology Group (ECOG) performance status of 0 or 1
- Life expectancy of \geq 26 weeks
- Body weight >30 kg

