3. STUDY DESIGN

3.1 Overview of study design

This is a Phase Ib open-label, single-arm study in newly diagnosed stage I-IIIA NSCLC patients, to test sirolimus in combination with durvalumab as neoadjuvant treatment prior to curative-intent surgical resection. The safety and tolerability as well as efficacy of combination sirolimus with durvalumab will be evaluated in this treatment setting. The study is also designed to investigate a number of laboratory correlative studies to define mechanisms of anti-tumor activity of sirolimus + durvalumab and several potential predictive biomarkers, which will help identify patients who are more likely to respond to treatment. Finally, the study will also include DFS and OS as secondary endpoints.

Up to 31 patients with NSCLC will be enrolled in this study at Emory University Winship Cancer Institute and affiliated sites. Enrollment will occur in 2 parts based on Simon 2 stage design, in which at least 2 of the first 16 patients must achieve pathologic complete response in order for the study to enroll 15 additional patients.

Eligible patients will complete 2 cycles of outpatient study treatment prior to proceeding to standard of care surgical resection. In order to allow a reliable assessment of the contribution of sirolimus versus durvalumab to the observed clinical and PD outcome, treatment will start with sirolimus 6mg orally for one loading dose followed by 2mg orally once daily three weeks prior to the start of durvalumab. Durvalumab will be administered at a dose of 1500mg Q 3 weeks starting on C1D1 for up to 2 cycles that are 21 days in length. Pharmacodynamic analysis will be done using PD samples collected at baseline (tissue) and with blood samples on day -7, C1D1 prior to durvalumab, C1D8, C2D1, C2D8 and at the time of surgery (blood and tissue). Additional post surgery blood samples will be collected at 1, 3, and 6 months post-surgery. See **study schedule of assessments** for schedule of Biomarker collection. Patients will proceed to surgery within a 4-week period post 2nd dose of durvalumab but not earlier than one week after the administration of durvalumab i.e. not earlier than C2D8. Additionally, patients will self-administer heavy water (D2O) 50ml orally three times a day from C1D1 through C1D5 followed by 50ml orally twice a day through the day prior to surgery in order to label dividing cells for research tracking purposes.

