5.3 Heavy Water (D2O)

Deuterated water is 70% D2O and 30% normal H2O and is manufactured and supplied by Cambridge Isotope Laboratories. The Emory research pharmacy will steriley portion out individually labeled 50ml conical tubes and provide to trial patients who agree to optional heavy water labelling study. Patients will self-administer 50 ml orally TID for the first 5 days to serve as

Clinical Study Protocol

Investigational Drug Substance: MEDI4736 Sirolimus (Rapamune)

Study Number **19-20015**

Edition Number: 4

Date: **11 February 2022**

a loading dose (Day 22, C1 Durvalumab). Subsequently, patients will self-administer 50 ml orally BID from day 27 until the day prior to surgery. Previous and ongoing studies have shown high compliance among donors. Since compliance with drinking the heavy water is critical to achieve adequate deuterium enrichment of body water, participants will be encouraged and rewarded for completing the memory aid provided (See **Appendix 5**) to help keep track of the heavy water consumption.

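### The heavy-water sub-study has two start days and two loading lengths, and its 42-day supply fits the synopsis surgery window but not the one in Section 3.1

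*Combined protocol and SAP*

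**What the plan says.** Five places describe the same labelling period.

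- **Synopsis, Study Design:** an optional study, with intake "50ml orally three times a day from day 22 C1 through day 27", then twice daily through the day before surgery. Surgery falls 2 to 3 weeks after the second durvalumab dose.
- **Section 3.1:** "patients will self-administer heavy water (D2O) 50ml orally three times a day from C1D1 through C1D5", then twice daily through the day before surgery. The word optional does not appear here. Surgery may fall 1 to 4 weeks after the second dose.
- **Section 5.3:** for patients who agree, "50 ml orally TID for the first 5 days to serve as" a loading dose tied to day 22; after that, "patients will self-administer 50 ml orally BID from day 27 until the day prior to surgery".
- **Section 8.1.2:** "first dose to be taken in clinic on day 23 and a 6 week supply". The entry gives no end day and does not say optional. The next item in the same list starts durvalumab on day 22.
- **Appendix 5:** a 42-row log with three doses on rows 1 to 5 and two doses from row 6.

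The Schedule of Assessments, inclusion criterion 13 and Section 1.5.1.2 all call the labelling optional. Under Deuterium Label Analysis, Section 8.2.2 measures proliferation of sorted T-cell subsets, from blood and surgical tissue, over the period in which deuterium is incorporated.

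**The concern.** In a labelling study the exposure window is part of the measurement. The labelled fraction in a T-cell subset depends on when label became available relative to durvalumab, how quickly body water was enriched, and whether enrichment held until the tissue was taken. If these differ because staff or patients followed different sections, differences in labelled fraction mix biology with exposure. A late start can miss label in the first divisions after durvalumab. Label that runs out before surgery under-counts the last divisions before resection. Section 5.3 itself treats compliance as critical to adequate enrichment.

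**Working it through.** **Day count.** Inputs: durvalumab dose 1 on day 22, repeated at 3 weeks (Section 8.1.2), so dose 2 is on day 22 + 21 = 43. Intake runs to the day before surgery (synopsis, 3.1, 5.3). Days of intake = surgery day − first intake day.

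The plan's own figure first: the latest synopsis surgery day is 43 + 21 = 64, and 64 − 22 = 42 days = 6 weeks. The supply and the log reproduce exactly, with the last intake on day 63.

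| Surgery rule | Latest surgery day | Days needed, day-22 start | Days needed, day-23 start | Shortfall against 42 |
|---|---|---|---|---|
| Synopsis, 2–3 weeks | 64 | 42 | 41 | none |
| Synopsis, dose 2 three days late (43 + 3 = 46) | 46 + 21 = 67 | 45 | 44 | 3 or 2 |
| Section 3.1, up to 4 weeks | 43 + 28 = 71 | 49 | 48 | 7 or 6 |

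The second row uses the Schedule's ±3-day tolerance on day 43 and its footnote that later visits move with a delayed cycle 2.

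**Loading length.** Synopsis: 27 − 22 + 1 = 6 days. Section 3.1: C1D1 to C1D5, days 22 to 26, 5 days. Section 5.3: twice daily from day 27, so days 22 to 26, 5 days. Appendix 5: 5 rows. Day 27 is therefore three doses in the synopsis and two in Section 5.3.

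**Effect on body-water enrichment.** From Section 5.3: 50 mL per dose, 70% D2O, so 3 × 50 × 0.70 = 105 mL/day while loading and 2 × 50 × 0.70 = 70 mL/day after. Assumed, not in the documents: body water V = 40 L and turnover k = 0.07 to 0.10 per day. Excess enrichment on day t is E(t) = E(t−1)·exp(−k) + D(t)/V. V cancels in every ratio below, so the results depend on k and not on the 40 L.

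| Comparison | Local effect (k = 0.07; 0.10) | Whole-window effect (k = 0.07; 0.10) |
|---|---|---|
| Start one day later, 5-day load | mean of days 22–28: −21.6%; −20.9% | 42-day mean: −3.1%; −2.8% |
| Six loading days instead of five | day-6 level: +7.0%; +7.6% | 42-day mean: +1.5%; +1.4% |
| Intake stops after 42 of 49 days | level on day 49: 60%; 49% of continued intake. Last-week mean: −24%; −32% | 49-day mean: −4.4%; −5.3% |

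Check on the last row: seven days without intake leave exp(−7k) = 0.61 (k = 0.07) or 0.50 (k = 0.10) of the day-42 level, slightly more than the ratios shown because continued intake would still be rising. Other daily discretisations move the last-row local figures by about two points at most.

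**The case against.** Much of the other side stands.

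- **Mandatory labelling.** A reader might infer from Sections 3.1 and 8.1.2 that all patients are labelled. The documents do not support this: those two sections only omit a word that the synopsis, Schedule, criterion 13, Section 1.5.1.2 and Section 5.3 supply.
- **Supply too short as such.** A reader might infer that the 6-week supply is wrong in itself. It matches the synopsis window to the day. The 6- to 7-day gap follows from the contradiction between the synopsis and Section 3.1 surgery windows, and the documents are silent on resupply. What remains is that the match has no reserve for a delayed second dose.
- **Day 23 may be one slip.** Section 8.1.2 also puts the sirolimus trough on day 23, where Section 8.2.3 has day 22. Its heavy-water dose is taken in clinic, yet the Schedule has no separate day-23 visit. That is plausible, but 8.1.2 is the procedural text that staff would follow.
- **Local effects overstate the damage.** This is fair. Over the whole window the changes are about 1 to 5%. The synopsis window alone already lets labelling run from 35 to 42 days, so unequal exposure is built in.
- **The remedy partly exists.** The log records dated intake, and Section 8.2.2 allows enrichment to be measured in saliva, urine or blood. However, the log as reproduced prompts saliva only on labelling days 7 and 14, which would not show a fall near surgery, and no analysis method is stated.

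**Conclusion.** The concern holds as an internal inconsistency of low severity. The start day (22 or 23) and the loading length (6 or 5 days) contradict each other across sections in the current text. Optional status is stated unevenly but is not contradicted. Supply and log fit one of the two stated surgery windows and not the other.

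For enrichment, the size is modest over the full window and larger at its edges: roughly a fifth in the first week for a one-day later start, and about half to three-fifths of the intended level on the day before surgery if intake stops seven days early. These figures rest on the assumed 7 to 10% daily turnover. They describe body water, not the labelled fraction in cells, which also depends on when cells divide. A reader might infer that the proliferation results would be uninterpretable; the whole-window changes of about 1 to 5% do not support that. Nothing here touches pathologic complete response, the safety analyses or the two-stage decision rule.

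**What to change.** Reconcile the synopsis, Sections 3.1, 5.3 and 8.1.2 and Appendix 5 on start day, loading length, optional status, end of intake and surgery window. Which version is right is for the sponsor to decide. Then make the dispensed supply and the log cover the reconciled labelling period, including permitted delays to cycle 2 and surgery.

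State in the analysis plan that the labelled fraction will be analysed using each patient's recorded first and last intake dates and measured body-water enrichment, with a measurement close to surgery.

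The cost is wording in four sections and the appendix. If the reconciled period were as long as 49 days, each affected consenting patient would need 14 more tubes (with a 5-day load, 5 × 3 + 44 × 2 = 103 against 5 × 3 + 37 × 2 = 89) and seven more log rows.
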